4.4.4 Other safety measurements and variables

4.4.4.1 Methods of assessment

Vital signs

Supine and standing blood pressure (mmHg) and pulse (bpm) will be measured. Supine blood pressure will be measured after 5 minutes in the supine position. Standing blood pressure will be measured after 2 minutes standing.

Supine and standing blood pressure and pulse measurements will be taken at the following timepoints:

Visit 1 (enrolment).

Visits 2 and 3: pre-dose, 1, 2, 4, 12 and 24 hours post-dose.

Visits 4, 5 and 6: pre-dose, pre-activation, 1 (standing only), 2 (standing only), 4 (standing only), 12 (standing only) and 24 hours post-activation.

Visit 7 (follow-up).

Blood pressure and pulse will be recorded using a semi-automatic blood pressure recording device (Omron) with an appropriate cuff size.

12-lead ECG

A 12-lead ECG and rhythm strip will be recorded at the following timepoints:

Visit 1 (enrolment).

Visits 2 and 3: pre-dose, 1, 2, 4, 12 and 24 hours post-dose.

Visits 4, 5 and 6: pre-dose, pre-activation, 1, 2, 4, 12 and 24 hours post-activation.

Visit 7 (follow-up).

The ECG will be performed using an automated machine (Schiller) which is programmed to provide an electronic interpretation of the electrocardiogram. These reports may be qualified by the investigator since the programme cautiously overstates potential abnormalities. A medically qualified person will assess the ECG parameters, and make an overall evaluation. Data obtained from the ECG traces (PR, QRS, QT, QTc interval, sinus rhythm, overall evaluation and any comments) will be directly entered into the study database by Data Management personnel, AstraZeneca R&D Charnwood.

Physical examination

Physical examinations will be performed at enrolment (Visit 1) and at the post-study follow-up visit (Visit 7). A medically qualified person will perform this examination.

4.5 Pharmacokinetic measurements and parameters

4.5.1 Summary of pharmacokinetic objectives and endpoints

Table 4 shows how the pharmacokinetic endpoints of this study relate to the study objectives.

Table 4 Pharmacokinetic objectives and endpoints relating to each objective

Objective	Endpoints	Summary statistic for analysis (including timepoint and population)	Planned analysis	Significance of results
Comparison of PK parameters of AZD6140 and the metabolite AR-C126910XX when released into proximal and distal small bowel and ascending colon	Plasma concentration of AZD6140 and the metabolite AR-C126910XX	Concentration data, C_{max} , t_{max} , AUC , AUC_{0-t} , $t_{1/2}$	Subjective comparison, graphical representation of AZD6140 and the metabolite AR-C126910XX concentration versus time	Comparison of the AZD6140 and metabolite concentrations will show the degree to which the oral suspension/powder is absorbed from different sites of the gut
Comparison of PK parameters of AZD6140 and the metabolite AR-C126910XX given as an IR tablet and an oral suspension	Plasma concentration of AZD6140 and the metabolite AR-C126910XX	Concentration data, C_{max} , t_{max} , AUC , AUC_{0-t} , $t_{1/2}$	Subjective comparison, graphical representation of AZD6140 and the metabolite AR-C126910XX concentration versus time	Comparison of the AZD6140 and metabolite concentrations will show whether the IR formulation is suitable for progressing to Phase II

The methods for collection of biological samples and derivation of pharmacokinetic parameters are presented below.

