There will be 5 treatment limbs. On each limb subjects will receive a single dose of study treatment. The first 2 study periods will last approximately 24 hours. The third, fourth and fifth study periods will last approximately 28, 31 or 48 hours, depending on the treatment allocation. Subjects will be required to return to the clinical unit at 36 hours either post-dose or post-activation for all regimens. Each capsule administration will be separated by a washout period of no less than 96 hours.

Endpoints

- Pharmacodynamic

Scintigraphic imaging – Gastric emptying time, small intestinal transit time, ileo-caecal junction (ICJ) arrival time, residence time at ICJ, colon arrival time, colon transit time, total transit time, time and anatomical location on successful Enterion activation.

- Safety

Haematology, clinical chemistry, urinalysis, blood pressure, pulse, 12-lead ECG and adverse events.

- Pharmacokinetic

The plasma concentration data for AZD6140 and the metabolite AR-C126910XX will be analysed using standard pharmacokinetic methods to yield the following parameters:

AUC, AUC_t, t_{1/2}, C_{max}, t_{max}.

Individual and mean plasma concentrations and pharmacokinetic parameters will be summarised and presented in tabular format and/or graphically by AstraZeneca R&D Charnwood. Descriptive statistics will be applied to the data.

Statistical methods

All data will be summarised using suitable summary statistics, where appropriate. No formal statistical analysis will be performed on any of the data.

	PAGE
PROTOCOL SYNOPSIS.....	2
LIST OF ABBREVIATIONS AND DEFINITION OF TERMS	9
1. INTRODUCTION.....	11
1.1 Background	11
1.2 Rationale for this study.....	12
2. STUDY OBJECTIVES	12
2.1 Primary objective	12
2.2 Secondary objectives.....	12
3. STUDY PLAN AND PROCEDURES.....	12
3.1 Overall study design and flow chart.....	12
3.2 Rationale for study design, doses and control groups.....	15
3.3 Selection of study population	15
3.3.1 Study selection record	15
3.3.2 Inclusion criteria.....	16
3.3.3 Exclusion criteria.....	16
3.3.4 Discontinuation of subjects from treatment or assessment	18
3.3.4.1 Criteria for discontinuation	18
3.3.4.2 Voluntary discontinuation by a subject.....	18
3.3.4.3 Incorrectly enrolled or randomised subjects	18
3.3.4.4 Procedures for discontinuation.....	19
3.3.5 Restrictions.....	19
3.3.5.1 Dietary restrictions	19
3.3.5.2 Activity restrictions	19
3.4 Treatments.....	20
3.4.1 Investigational products	20

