3.2 Rationale for study design, doses and control groups

The study's open design is to optimise the number of volunteers completing each segment of the study. Crossing over the release sites for the Enterion allows some flexibility in that, if a site is missed by rapid passage beyond that site, drug can be delivered at a lower site and the randomisation changed to allow the next limb to dose at the earlier GI site. Similarly, by crossing over the tablet and suspension as the first 2 limbs of the study, baseline pharmacokinetic data will be obtained for the majority of subjects and maximise the numbers receiving both tablet and suspension.

The dose selected was restricted by the size of the drug chamber in the Enterion capsule. A dose of 100 mg was selected as the best dose to fit into the chamber and also that which is predicted to give evaluable PK data out to the 36-hour timepoint (ie with approximately 30% of the exposure, 36-hour concentrations of AZD6140 will be greater than the Limit of Quantification of the assay).

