4.5.2.2 Faecal sampling

From the time of dosing all subjects will be instructed to collect all faecal samples (Visits 4, 5 and 6 only). If the capsule has not been passed prior to the subject leaving the unit, the subject will be instructed to bring all samples to the unit each day until the capsule has been recovered. Once recovered the capsule will be visually examined to confirm that the drug has been released. It will then be stored at -20°C until dispatch for residual drug analysis or for disposal.

4.5.3 Drug concentration measurements, and calculation or derivation of pharmacokinetic parameters

The plasma concentration data for AZD6140 and the metabolite AR-C126910XX will be analysed using standard pharmacokinetic methods to yield the following parameters:

AUC, *AUC_t*, *t*_{1/2}, *C*_{max} and *t*_{max}.

The pharmacokinetic evaluation will be carried out by, or under the guidance of, the Clinical Pharmacokinetic Section of the Department of Experimental Medicine at AstraZeneca R&D Charnwood, using an appropriate pharmacokinetic software package. Non-compartmental methods will be used if appropriate.

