6. STATISTICAL METHODS AND DETERMINATION OF SAMPLE SIZE

6.1 Determination of sample size

No formal sample size calculations were performed. The sample size of 10 subjects was deemed to be adequate to provide definitive information on plasma concentrations of AZD6140.

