6.2.3 Statistical analyses

All pre-treatment group characteristics will be summarised and presented using standard summary statistics. No statistical hypothesis tests will be carried out on baseline data.

No formal statistical tests will be done on any pharmacokinetic data. The plasma concentration data will be summarised, by timepoint. PK parameters will be calculated for each subject, and summarised by treatment limb. Individual and mean plasma concentrations and pharmacokinetic parameters will be summarised and presented in tabular format and/or graphically. Descriptive statistics will be applied to the data.

Adverse Events

Adverse events will be summarised by System Organ Class and Astra Preferred Term, using Astra Adverse Event Terminology. All adverse events will be noted as being emergent during pre-treatment (prior to any study drug being given to the subject), or treatment-emergent (if they appear following administration of study drug). If an adverse event is treatment-emergent, it will be assumed to be emergent due to the last dose level having been administered to that subject.

All adverse event data will be listed for all subjects. Separate listings of all serious adverse events, deaths or other significant adverse events, as assessed by the study responsible physician, will be presented.

Adverse event data will be summarised by causality (whether there is a reasonable possibility that the event is causally related to study drug 'Yes' or 'No') and intensity, and by causality and seriousness, by treatment emergence category. Summaries will be presented by treatment limb.

Laboratory data

All laboratory safety data, incorporating haematology, clinical chemistry and urinalysis data, will be listed, with deviations from the normal ranges explicitly noted on the listings.

Numerical laboratory safety data will be summarised using standard summary statistics by scheduled timepoint. Raw values will be summarised for the Visit 1, pre-dose baseline measurements and follow-up measurements, and within-subject changes from baseline for the post-treatment measurements. Summaries will be presented by treatment limb.

Discrete laboratory safety data will be summarised showing the number of subjects at each level of measurement at each scheduled timepoint. These summaries will be presented by treatment limb.

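### The PK comparisons of release sites and of tablet with suspension are planned as subjective, so the protocol calls for no within-subject exposure ratio and no interval

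*Protocol*

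**What the plan says.** Both rows of Table 4 (protocol section 4.5.1) carry the same planned analysis: "Subjective comparison, graphical representation of AZD6140 and the metabolite AR-C126910XX concentration versus time". One row covers the proximal small bowel, distal small bowel and ascending colon, which is the primary objective in section 2.1. The other covers tablet against suspension, the first secondary objective in section 2.2.

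Section 6.2.3 states "No formal statistical tests will be done on any pharmacokinetic data" and "PK parameters will be calculated for each subject, and summarised by treatment limb". The synopsis goes further: "No formal statistical analysis will be performed on any of the data". Under section 4.5.3 the concentrations are "analysed using standard pharmacokinetic methods to yield the following parameters": AUC, AUC_t, half-life, Cmax and tmax. No relative bioavailability, ratio or interval is named anywhere in the protocol.

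For the tablet, the last column of Table 4 says: "Comparison of the AZD6140 and metabolite concentrations will show whether the IR formulation is suitable for progressing to Phase II". For the sites, it says that the comparison will show the degree of absorption from each. On numbers, section 6.1 reports no formal calculation and adds: "The sample size of 10 subjects was deemed to be adequate to provide definitive information on plasma concentrations of AZD6140".

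**The concern.** Section 3.4.2 gives every subject a single dose of each of the five treatments. The main statistical return on that design is a within-subject contrast: how much of a subject's exposure from one site or formulation is achieved with another. The degree of absorption by site is such a relative quantity, and suitability for Phase II is a decision that turns on one. The protocol names neither the quantity nor a measure of its uncertainty, and it assigns the comparison to judgement by eye.

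At stake are two uses of the results: the design of a modified release tablet and the choice of the tablet for Phase II. Two readers of the same limb summaries and curves could reach different conclusions, and the plan gives no means of saying how far chance could account for a difference.

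**Working it through.** **No figure to reproduce.** Section 6.1 gives no CV, effect size, margin or precision target. The check is therefore (a) what the plan would deliver against what Table 4 says it will show, and (b) what precision the design could give.

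**(a) Claim against output**
- Table 4 claims the degree of absorption by site. The planned output is parameters summarised per limb, individual values, and curves compared subjectively.
- Table 4 claims a conclusion on whether the tablet suits Phase II. The planned output is the same, with no estimate, interval or criterion.
- Section 1.2 says regional absorption is to be compared with the suspension and with the tablet. Table 4 has no row for that comparison.

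**(b) Precision available**

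Inputs: n = 10, the minimum number of completers (section 3.1; at most 12 are dosed). The within-subject CV is not in the protocol; 20, 30 and 40% are assumed. The 90% confidence level is also an assumption.

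Formulas:
- s_w = √ln(1 + CV²), which gives 0.198, 0.294 and 0.385.
- Half-width on the log scale = t(0.95, df) × s_w × √(2/n), with √(2/10) = 0.447.
- Oral block, two periods: df = n − 2 = 8, t = 1.860.
- Capsule block, three periods: df = (3n − 1) − (n − 1) − 2 − 2 = 2n − 4 = 16, t = 1.746.

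Worked case, oral block at 20%: 1.860 × 0.198 × 0.447 = 0.165, and exp(0.165) = 1.18.

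| Assumed CV | Tablet/suspension, n = 10 | Site/site, n = 10 |
|---|---|---|
| 20% | ×/÷ 1.18 (84.8 to 117.9%) | ×/÷ 1.17 (85.7 to 116.7%) |
| 30% | ×/÷ 1.28 (78.3 to 127.7%) | ×/÷ 1.26 (79.5 to 125.8%) |
| 40% | ×/÷ 1.38 (72.6 to 137.8%) | ×/÷ 1.35 (74.0 to 135.1%) |

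The ranges in brackets are 90% confidence intervals around an observed ratio of 100%. With all 12 subjects the factors are 1.16, 1.24 and 1.33 (oral) and 1.15, 1.23 and 1.31 (capsule).

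**Which contrasts the design supports.** Tablet and suspension are randomised between Visits 2 and 3, and the three sites are randomised over Visits 4 to 6 (section 3.1). Contrasts inside each block can be adjusted for period. A capsule limb against the suspension cannot be separated from three other differences:
- oral doses always come first;
- oral doses are taken fasted, while capsule visits include a light breakfast about 4 hours before dosing (section 3.3.5.1);
- the capsule may hold powder instead of suspension (section 3.4.1.1).

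A period term within block does not remove these differences.

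**The case against.** The best defence is that this is a small exploratory Phase I study. Its primary endpoint is a concentration profile (section 4.1), its primary objective is to aid a formulation design, and graphs suit that purpose. Section 6.2.1 leaves its list of summary statistics open and defers to a statistical analysis plan that is not at hand. Much of this stands: hypothesis tests are not needed, and descriptive work is legitimate here. But Table 4 itself fixes the comparison as subjective and the synopsis rules out formal analysis, so an analysis plan that added modelled ratios would depart from the protocol.

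Four stronger readings are tempting and are not supported.
- *The pairing is thrown away.* Section 6.2.3 also presents individual concentrations and parameters, so each subject's ratios can be formed by division. It is equally wrong to set the intervals above against an unpaired interval, because the protocol plans none.
- *The limbs will hold different subjects.* Section 3.4.2 allows for missed activations but also for reallocation and additional study days. Section 3.2 puts the oral limbs first to maximise the number receiving both. Imbalance is possible, not certain.
- *AUC_t is biased by a known amount at poorly absorbing sites.* Section 3.2 says that "with approximately 30% of the exposure, 36-hour concentrations of AZD6140 will be greater than the Limit of Quantification of the assay". That is a sufficient condition, not a cutoff, and no half-life is given. Total AUC is planned beside AUC_t. A shorter AUC_t window is a reasonable worry, but the protocol does not let its size be calculated.
- *Ten subjects are claimed to settle the formulation question.* The sentence in section 6.1 speaks of plasma concentrations, not of ratios or of the Phase II choice.

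**Conclusion.** The point holds in a limited form. For the primary objective and the first secondary objective, the protocol sets a subjective comparison with limb-by-limb summaries. It calls for no within-subject relative exposure and no measure of its uncertainty, while stating conclusions that depend on both. The data to do better will be collected anyway.

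On size, the design could support 90% intervals of about ×/÷ 1.18 to 1.38 for tablet/suspension and ×/÷ 1.17 to 1.35 for one site against another. This rests on 10 completers, an assumed within-subject CV of 20 to 40%, log-normal exposure and the randomised order being kept. Intervals this wide would show a large site effect but could leave a modest tablet difference unresolved, which readers of Table 4 should be able to see.

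This is a should-fix. Nothing in the protocol makes the planned summaries invalid.

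**What to change.** In Table 4, section 6.2.3 and the synopsis, replace the subjective comparison with estimation, and state that no hypothesis test is intended.
- Fit log-scale crossover models by treatment received, with subject and period effects, separately for the oral block (tablet/suspension) and the capsule block (distal/proximal and colon/proximal).
- Report geometric mean ratios with 90% confidence intervals for AUC and Cmax, plus individual ratios and paired tmax differences. Keep the graphs.
- Where AUC cannot be extrapolated reliably, add AUC over an interval common to that subject's limbs.
- Report capsule/suspension ratios as descriptive only, and say that they are confounded with visit block, fed state and possibly formulation.
- In section 6.1, replace the word definitive with the expected precision under stated assumptions, such as the factors above.

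The cost is protocol wording and a little programming, with no new subjects, samples or procedures. One limit remains: if capsule order is reallocated for rapid transit (sections 3.2 and 3.4.2), the capsule-block intervals become somewhat less precise than shown, and the report should say so.

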4.5.2 Collection of biological samples

4.5.2.1 Pharmacokinetic blood samples

Blood samples of 5.5 mL (4.5 mL for analysis, 1.0 mL discarded) for the determination of AZD6140 and the metabolite AR-C126910XX will be taken during the study at the following timepoints:

Visits 2 and 3:

Pre-dose and at 0.5, 1, 1.5, 2, 3, 4, 6, 8, 12, 18, 24 and 36 hours after dosing.

Visits 4, 5 and 6:

Pre-dose, pre-activation and 0.5, 1, 1.5, 2, 3, 4, 6, 8, 12, 18, 24 and 36 hours after activation.

See Section 7.6 for information on numbers of samples and blood volume.

Blood samples will be collected into lithium heparin tubes and placed on ice until centrifugation. The samples must be centrifuged (3000 rpm at 4°C for 10 minutes) within 30 minutes of sampling to obtain plasma. The resultant plasma will be transferred into a plain polypropylene tube (screw cap) and frozen upright at or below -20°C. All plasma samples must be labelled with the study number, subject number and study timepoint. The labels must maintain their integrity despite contact with moisture. The frozen samples will be shipped, on dry ice, on an ongoing basis for analysis under the guidance of AstraZeneca.

4.5.2.2 Faecal sampling

From the time of dosing all subjects will be instructed to collect all faecal samples (Visits 4, 5 and 6 only). If the capsule has not been passed prior to the subject leaving the unit, the subject will be instructed to bring all samples to the unit each day until the capsule has been recovered. Once recovered the capsule will be visually examined to confirm that the drug has been released. It will then be stored at -20°C until dispatch for residual drug analysis or for disposal.

4.5.3 Drug concentration measurements, and calculation or derivation of pharmacokinetic parameters

The plasma concentration data for AZD6140 and the metabolite AR-C126910XX will be analysed using standard pharmacokinetic methods to yield the following parameters:

AUC, *AUC_t*, *t*_{1/2}, *C*_{max} and *t*_{max}.

The pharmacokinetic evaluation will be carried out by, or under the guidance of, the Clinical Pharmacokinetic Section of the Department of Experimental Medicine at AstraZeneca R&D Charnwood, using an appropriate pharmacokinetic software package. Non-compartmental methods will be used if appropriate.

5. DATA MANAGEMENT

Data will be validated and quality checked by the AstraZeneca Monitor at the centre throughout the study. The original, edited CRFs will be returned to Data Management at AstraZeneca.

The data will be entered onto the AMOS database at AstraZeneca. The entered data will be manually checked against the originals and additional computerised checks will be run. Any missing, impossible or inconsistent entries in the CRF will be referred back to the investigator via the monitor within 3 working days of entering data using data query forms. Responses should be received and updated within 3 working days of generation.

Safety data comprising clinical chemistry, haematology and urinalysis will be reported by the department of Clinical Pathology at AstraZeneca R&D Charnwood and loaded into AMOS. Original paper printouts of the results will be sent to the study clinical investigator for comment and signature and then filed with the remainder of the CRFs.

Final quality control checks will be completed and error rates reported prior to a meeting to discuss the declaration of a clean data file. Protocol deviations detected during blind review of the data and during the data entry process will be considered for their effect on the analysis of the data. All decisions on the evaluability of data from each subject must have been made and documented in the Statistical Analysis Plan before declaration of clean file. The date of clean file will be documented within one day of the clean file meeting. The database will be locked and SAS® datasets will be extracted for the statistical analysis of the data.

6. STATISTICAL METHODS AND DETERMINATION OF SAMPLE SIZE

6.1 Determination of sample size

No formal sample size calculations were performed. The sample size of 10 subjects was deemed to be adequate to provide definitive information on plasma concentrations of AZD6140.

6.2 Statistical evaluation

6.2.1 Methods of statistical analysis

Statistical and safety analyses will be carried out by, or under the guidance of, the Statistics Department AstraZeneca R&D Charnwood. Statistical analyses will be performed according to the Statistical Analysis Plan. The Statistical Analysis Plan will be prepared before database lock.

Where standard summary statistics are referenced, these will include (but not be limited to) the mean, standard deviation, median, minimum and maximum for continuous data, and counts and frequency percentages for categorical data.

